#### 2.5.3 Handling of intercurrent events

The primary analyses will account for intercurrent events as explained in the following:

Participants who receive the investigational imaging agent [F]CTT1057 but do not undergo/complete the PET/CT scan for any reason (e.g. consent withdrawal, PET camera failures, etc.) will not be used for the co-primary endpoint analyses. Note that safety data for these participants will be collected after the administration of the investigational imaging agent and will be summarized.

#### 2.5.4 Handling of missing values not related to intercurrent event

This is a diagnostic study, where the co-primary endpoints are calculated on the basis of a one-time imaging assessment. Missing data will not be imputed.

#### 2.5.5 Sensitivity analyses

For participants where CTS Level 1 or 2 is used as the truth standard for the primary analysis, the next lower level of CTS will be used to verify positivity or negativity for the sensitivity analysis, if available. For instance, if pathology (CTS Level 1) is used for a lesion as the truth standard for the primary estimand, the imaging component of CTS (Level 2) will be used as truth standard for sensitivity analysis for the primary estimand. Similarly, results of CTS Level 2 will be replaced by CTS Level 3 if applicable. However, for those using changes in PSA level (CTS Level 3) as the truth standard for primary estimand, their positivity status cannot be replaced by another component of CTS for sensitivity analysis.

Region-level CLR along with its 95% CI will also be computed based on the weighted estimator approach (Lee and Dubin 1994) for each central reader as following:

$$\hat{p}_w \pm 1.96 \hat{\sigma}/\sqrt{n}$$
.

 $\hat{p}_w$  is the point estimator with  $\hat{p}_w = \sum_{i=1}^n \hat{p}_i / n$  and  $\hat{p}_i = y_i / n_i$ , where  $y_i$  and  $n_i$  are the same as defined in Section 2.5.2 above and n represents the number of participants with at least one PET-positive finding by central assessments.  $\hat{\sigma}$  is the estimated standard deviation of  $\hat{p}_i$ .

#### 2.5.6 Supplementary analyses

Supplementary analyses for region-level CLR and patient-level PPV will be performed for the following subgroups:

- Initial definitive therapy received:
  - o prior radical prostatectomy
  - o prior curative intent radiation therapy
- PSA level at baseline (from central laboratory):

- $PSA \le 0.5 \text{ ng/mL}$
- $\circ$  0.5 ng/mL<PSA $\leq$ 1 ng/mL
- $\circ$  1 ng/mL<PSA $\leq$ 2 ng/mL
- $\circ$  2 ng/mL<PSA $\leq$ 5 ng/mL
- $\circ$  PSA > 5 ng/mL

In addition, estimates of region-level CLR and corresponding 95% CI will be obtained from the logistic random-effects regression model, adjusting for covariates and taking into account the correlation among regions within one participant; while estimates of patient-level PPV and corresponding 95% CI will be obtained from the logistic regression model adjusting for covariates. Candidate covariates include categorized PSA level at baseline (from central laboratory) and the initial definitive therapy received (with either RP or curative-intent RT) as given above. The p-values from the Type III tests for each candidate covariate in the full model will be provided. The region-level CLR and patient-level PPV (and their 95% CIs) for each level of the covariates estimated from the full model including all candidate covariates, as well as the final model including only statistically significant covariates (p-value < 0.05), will be displayed. In the case there are no statistically significant covariates identified from the full model, the region-level CLR (and 95% CI) from the unadjusted logistic regression model and the patient-level PPV (and 95% CI) from the unadjusted logistic regression model will be provided.

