Evaluate detection rate	 Proportion of patients who have at least one PET positive lesion, regardless of TP or FP findings, out of all patients who are scanned 		
Evaluate the region level sensitivity of [18F]CTT1057	 Proportion of regions that test positive on both [18F]CTT1057 and CTS (TP) among those regions that are CTS positive (TP or FN) 		
Evaluate the region level specificity of [18F]CTT1057	Proportion of regions that test negative on both [18F]CTT1057 and CTS (TN) among those regions that are CTS negative (FP, or TN)		
Evaluate the region level negative predictive value of [¹⁸ F]CTT1057	Proportion of regions that are CTS and [18F]CTT1057 negative (TN) among those regions that test negative on [18F]CTT1057 (TN or FN)		
Evaluate the region level accuracy of [18F]CTT1057	 Proportion of regions that are CTS and [¹8F]CTT1057 positive (TP) and negative (TN) among those regions that identified on [¹8F]CTT1057 (TP, TN, FP and FN) 		
Evaluate the patient-level positive predictive value related to PSA levels	Percentage of patients who have at least one TP lesion (exactly anatomically localized correspondence between [¹8F]CTT1057 PET imaging and the reference standard), regardless of any co-existent FP findings, out of all patients who are [¹8F]CTT1057 positive, stratified by PSA levels		
Characterize the safety and tolerability of [18F]CTT1057	Incidence of AEs Treatment emergent adverse event (TEAE) rate within 14 days after each PET tracer administration		

Amended Protocol (Version No.	01 Clean)
Allieliaea i Totocoi (VEISION INC	. U i Cicaii)

Objective(s)	Endpoint(s)	
• [¹⁸ F]CTT1057 scan inter-reader variability	Inter-reader agreement of [18F]CTT1057 images	
• [¹⁸ F]CTT1057 scan intra-reader variability	Intra-reader agreement of [18F]CTT1057 images	
 Concordance between [¹⁸F]CTT1057 and [⁶⁸Ga]Ga-PSMA-11 for detection of lesions at lesion level using central reads 	Concordance between [18F]CTT1057 and [68Ga]Ga-PSMA-11 for detection of PSMA-positive lesions (location and number) using central reads	
 Evaluate the change in patient management plans attributed to the PET/CT scan 	Percentage of patients who underwent a change in intended treatment plan attributed to the PET/CT scan as assessed by pre and post imaging questionnaires	

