5.1 Inclusion criteria

Participants eligible for inclusion in this study must meet all of the following criteria:

- 1. Signed informed consent must be obtained prior to participation in the study
- 2. Biopsy proven prostate adenocarcinoma.

3a. Biochemical recurrence following initial definitive therapy (with either RP or curative intent radiation therapy) as defined:

- by AUA criteria (Cookson et al 2007) for patients who have undergone RP: Initial serum PSA of ≥0.2 ng/ml measured at least 6 weeks after RP with a second confirmatory persistent PSA level of >0.2 ng/ml, or
- by ASTRO-Phoenix criteria (Roach et al 2006) for patients who have undergone curative-intent radiation therapy (RT): Rise of serum PSA measurement of 2 or more ng/mL above the nadir PSA observed post RT.
- 4. ECOG performance status 0-2
- 5. Participants must be adults ≥ 18 years of age

5.2 **Exclusion criteria**

Participants meeting any of the following criteria are not eligible for inclusion in this study.

- 1. Inability to complete the needed investigational and standard-of-care imaging examinations due to any reason (severe claustrophobia, inability to lie still for the entire imaging time, etc.)
- 2. Any additional medical condition, serious intercurrent illness, concomitant cancer or other extenuating circumstance that, in the opinion of the Investigator, would indicate a significant risk to safety or impair study participation, including, but not limited to, current severe urinary incontinence, hydronephrosis, severe voiding dysfunction, need of indwelling/condom catheters, New York Heart Association class III or IV congestive heart failure, history of congenital prolonged QT syndrome, uncontrolled infection, active hepatitis B or C, and COVID-19
- 3. Prior major surgery undergone less than 12 weeks prior to screening (with the exception of any surgery related to prostatic cancer)
- 4. Known allergy, hypersensitivity, or intolerance to [18F]CTT1057, [68Ga]Ga-PSMA-11, or to CT contrast
- 5. Prior and current use of PSMA targeted therapies
- 7a. Prior ADT (first or second generation), including LHRH analogues (agonists or antagonists), within 9 months before screening
- 8. Any 5-alpha reductase inhibitors within 30 days before screening
- 9. Use of other investigational drugs within 30 days before screening
- 10. Castration-resistant patients

- 11. Patient with small cell or neuroendocrine PCa in more than 50% of biopsy tissue

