- 12. Prior salvage surgery or salvage radiation therapy

6 **Treatment**

6.1 **Study treatment**

The term "Study Treatment" indicates the administration of at least one of the two PET imaging agents: [18F]CTT1057 and [68Ga]Ga-PSMA-11 independently of whether the PET/CT scans were acquired or not. In this study, the investigational imaging agent of interest is the radioligand imaging compound [18F]CTT1057. [68Ga]Ga-PSMA-11 will be used as a component of the CTS Level 2 if required, and in all participants for the secondary endpoint of assessment of concordance between [18F]CTT1057 and [68Ga]Ga-PSMA-11 for detection of lesions (as detailed in Section 2).

Participants will be administered both agents at least 2 weeks (14 days) apart as an intravenous injection (Refer to Section 6.7 for study drug preparation and dispensation) according to the randomly assigned PET/CT scan sequence after enrolment.

Participants will be administered [18F]CTT1057 and [68Ga]Ga-PSMA-11 as an intravenous injection, single dose (Refer to Section 6.7 for study drug preparation and dispensation). Both agents will be provided by Novartis.

The general doses of the study treatment are listed in Section 6.1.

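### Eligibility leaves the PSA strata up to 2 ng/mL almost entirely prior-prostatectomy, so the p<0.05 final model and any PSA-level estimate averaged over therapy in SAP 2.5.6 can mislead

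*SAP*

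**What the plan says.** **Eligibility.** Protocol 5.1, criterion 3a, sets different PSA floors by prior therapy. After radical prostatectomy (RP): "Initial serum PSA of ≥0.2 ng/ml measured at least 6 weeks after RP", with a confirmatory value above 0.2. After curative-intent radiotherapy (RT): "Rise of serum PSA measurement of 2 or more ng/mL above the nadir PSA observed post RT". Exclusion 12 in Protocol 5.2 ("Prior salvage surgery or salvage radiation therapy") helps keep the two groups distinct.

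**Subgroups.** SAP 2.5.6 lists CLR and PPV by prior therapy and, separately, by five strata of central-laboratory baseline PSA: up to 0.5, 0.5-1, 1-2, 2-5 and above 5 ng/mL. SAP 2.6.6 applies the same PSA strata to the secondary diagnostic parameters.

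**Models.** SAP 2.5.6 also fits covariate-adjusted models: "Candidate covariates include categorized PSA level at baseline (from central laboratory) and the initial definitive therapy received". No interaction is mentioned. Type III p-values are given, and estimates for each covariate level are shown as "estimated from the full model including all candidate covariates" and again from "the final model including only statistically significant covariates (p-value < 0.05"). If neither covariate is significant, the unadjusted estimate is provided. The SAP does not say how an estimate for one PSA level treats the other covariate.

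**Objectives.** Protocol Table 2-1 and SAP Table 1-1 include "Evaluate the patient-level positive predictive value related to PSA levels". Their last row asks for all primary and secondary endpoints separately in the RP and RT subgroups. SAP 2.2.1 and SAP 4 keep this for the efficacy endpoints.

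**The concern.** PSA stratum and prior therapy are tied by the entry criteria, and the SAP does not say so. An RT patient's qualifying PSA is at least nadir plus 2, so below 2 ng/mL there is almost nobody with prior RT, while above 2 ng/mL the two therapies are mixed. A one-factor PSA summary therefore cannot tell a PSA effect from a therapy effect.

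The adjusted models are where a reader would look to separate the two. Selecting covariates by p-value can remove the therapy term that does the separating, and the intervals then take no account of the selection. Averaging a low-PSA estimate over both therapies gives a figure for a combination that essentially does not occur. Performance at low PSA would be easy to misread.

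**Working it through.** **Step 1. Number of PET-positive patients.** From SAP 3.1: 152 × 0.80 = 121.6, so 122. An exact one-sided binomial test of 0.20 against 0.33 with n = 122 rejects at 34 or more, with alpha 0.0228 and power 90.5%. This reproduces the stated 90%. No sample-size figure is disputed; 122 is what the supplementary PPV models have to work with.

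**Step 2. Overlap.** The documents give neither the RT share nor the PSA spread. Assumption set A: RT is 15-40% of PET-positives; RP is spread 30/20/20/15/15% over the five strata; RT is split equally between 2-5 and above 5. Three of the ten PSA-by-therapy cells are then empty. RT share in each stratum above 2:

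- RT 15%: 0.075 / (0.1275 + 0.075) = 0.37
- RT 40%: 0.20 / (0.09 + 0.20) = 0.69

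Expected PET-positives per RT cell are 122 × share / 2: about 9, 15 and 24 at RT shares of 15%, 25% and 40%.

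**Step 3. Pooled PSA strata under a therapy effect only.** Stratum PPV = PPV(RP) + RT share × difference.

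| Assumed inputs | RT share | Each stratum up to 2 | 2-5 | Above 5 |
|---|---|---|---|---|
| A: PPV 0.30 RP, 0.50 RT | 15% | 0.30 | 0.37 | 0.37 |
| A: same | 40% | 0.30 | 0.44 | 0.44 |
| B: PPV 0.60 RP, 0.80 RT | 15% | 0.60 | 0.66 | 0.69 |
| B: same | 35% | 0.60 | 0.71 | 0.75 |

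Set B spreads RP 30/20/20/20/10% and splits RT equally above 2. With no PSA effect at all, the gradient from the lowest to the highest stratum is about 7-15 points.

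**Step 4. Can the full model separate the two?** Yes, given additivity. The main-effects design has full rank (6 of 6) despite the empty cells. Fitted to expected counts under set A (RT 25%, therapy effect only), it returns PSA coefficients of 0 and a therapy log odds ratio of 0.847 (SE 0.552). The therapy term is identified only from patients above 2 ng/mL, so additivity cannot be checked below that.

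**Step 5. Level estimates averaged over therapy.** These use the same correctly specified model, averaged on the logit scale.

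- Set B, equal weights: expit[(0.4055 + 1.3863)/2] = expit(0.896) = 0.71
- Set B, observed weights (35% RT): expit(0.4055 + 0.35 × 0.9808) = expit(0.749) = 0.68
- Set A, equal weights: expit[(−0.847 + 0)/2] = 0.40

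The true values for patients who exist at low PSA are 0.60, 0.60 and 0.30. Predicted for RP patients instead of averaged, the same model gives the right answer.

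**Step 6. The p<0.05 rule.** From Step 4, the expected z for therapy is 0.847/0.552 = 1.53, so the chance of passing 1.96 is roughly Φ(1.53 − 1.96) = Φ(−0.43) = 0.33. Simulation of that case (1,500 runs, 122 patients, likelihood-ratio tests standing in for Type III tests) dropped therapy in 0.039 + 0.617 = 66% of trials. A second set of simulations let RP PPV rise with PSA (0.20, 0.25, 0.30, 0.40, 0.50) and added a true therapy effect, with RT share 15-40%:

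| Therapy log odds ratio | Therapy dropped | Final model has PSA only |
|---|---|---|
| 0.4 | 86-88% | 34-40% |
| 0.7 | 73-78% | 30-38% |
| 1.1 | 46-55% | 23-30% |

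When PSA alone survives, the expected estimates are 0.44-0.58 at 2-5 and 0.54-0.67 above 5, against RP values of 0.40 and 0.50. Only PPV was simulated. The same selection rule applies to CLR, but its drop rate was not computed.

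**The case against.** The case on the other side is substantial.

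- **The full model is always shown, with its p-values.** A reader might infer that all the adjusted estimates mix PSA with therapy. The documents do not support that: both covariates are in the full model, and Step 4 shows that it separates additive effects. What stands against the plan is the second model and the unstated averaging.
- **Within-therapy PSA results are already implied.** A reader might infer that PPV by PSA is planned only pooled over therapy. The last row of the objectives tables, with SAP 2.2.1 and SAP 4, points the other way. However, SAP 2.5.6 and 2.6.6 list only one-factor PSA strata, SAP 2.6 omits PPV by PSA from its list, and CLR by PSA within therapy is not explicitly planned.
- **Pooled PPV by PSA is a legitimate description.** No document claims a causal PSA effect, so a mixed-stratum PPV is correct for that band of the enrolled population. This stands; the limit is on interpretation.
- **The tie is not absolute.** A PSA of exactly 2.0 with a nadir of 0 falls in the 1-2 stratum, and central baseline PSA may differ from the qualifying value. SAP 2.3.2 also summarises screening PSA separately by therapy, so limited overlap will be visible. Hence essentially RP-only, not RP-only by rule.
- **The averaging weights are not in the SAP.** Step 5 is therefore conditional on averaging over therapy.

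**Conclusion.** The concern holds in a limited form. Eligibility makes the strata up to 2 ng/mL essentially RP-only. Given that, the p<0.05 final model is a poor choice: it dropped a true therapy effect in about 46-88% of trials across the Step 6 effect sizes. In 23-40% it left PSA alone, with therapy-confounded level estimates and intervals that ignore the selection. Full-model PSA-level estimates, if averaged over therapy, extrapolate to a near-empty cell (0.68-0.71 against 0.60, or 0.40 against 0.30). Pooled PSA strata describe each band but cannot be read as a PSA effect, since a pure therapy difference produced a 7-15 point gradient.

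All these sizes depend on assumed RT share, PSA spread and PPVs, none of which the documents give. The direction depends on which therapy group has the higher PPV; the examples assume RT. Nor should a reader infer a threat to the study result: SAP 2.5.2 rests success on the unadjusted CLR and PPV of each reader, so the co-primary decision, alpha and sample size are unaffected.

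**What to change.** In SAP 2.5.6, delete the p<0.05 final model and its unadjusted fallback, and report the full model with both covariates. Report adjusted level estimates only for combinations that occur: RP at all five PSA levels and RT at the two levels above 2 ng/mL. State that the model assumes additivity.

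In SAP 2.5.6 and 2.6.6, carry out what the objectives tables imply. Tabulate counts, PPV and CLR (and the secondary parameters in 2.6.6) by PSA within RP and, for RT, in the strata above 2 ng/mL. Show any RT participant with a lower central PSA as a count only. Keep pooled PSA strata if wanted, with a note that the therapy mix changes at 2 ng/mL.

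The cost is SAP wording, with the same data and software. The downside is precision: under the assumptions above, each RT cell holds roughly 9 to 24 PET-positive patients, so intervals will be wide.

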•	Evaluate the region level sensitivity of [  F]CTT1057	•	Proportion of regions that test positive on both [18F]CTT1057 and CTS (TP) among those regions that are CTS positive (TP or FN)		
•	Evaluate the region level specificity of [  F]CTT1057	•	Proportion of regions that test negative on both [18F]CTT1057 and CTS (TN) among those regions that are CTS negative (FP, or TN)		
•	Evaluate the region level negative predictive value of [  F]CTT1057	•	Proportion of regions that are CTS and [18F]CTT1057 negative (TN) among those regions that test negative on [18F]CTT1057 (TN or FN)		
•	Evaluate the region level accuracy of [  F]CTT1057	•	Proportion of regions that are CTS and [18F]CTT1057 positive (TP) and negative (TN) among those regions that identified on [18F]CTT1057 (TP, TN, FP and FN)		
•	Evaluate the patient-level positive predictive value related to PSA levels	•	Percentage of patients who have at least one TP lesion (exactly anatomically localized correspondence between [18F]CTT1057 PET imaging and the reference standard), regardless of any co-existent FP findings, out of all patients who are [18F]CTT1057 positive, stratified by PSA levels		
•	Characterize the safety and tolerability of [18F]CTT1057	•	Incidence of AEs. Treatment emergent adverse event (TEAE) rate within 14 days after each PET tracer administration		
•	[  F]CTT1057 scan inter-reader variability	•	Inter-reader agreement of [18F]CTT1057 images		
•	[  F]CTT1057 scan intra-reader variability	•	Intra-reader agreement of [18F]CTT1057 images		

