#### **Patient-level PPV**

The null hypothesis (H0: patient-level PPV p = 0.20) will be tested against the alternative hypothesis (H1: p > 0.20). Assuming a patient-level PPV of 0.33 under the alternative hypothesis, a total sample size of 190 enrolled participants (which includes 152 [ $^{18}$ F]CTT1057 scanned participants based on 80% [ $^{18}$ F]CTT1057 positive patient rate) would achieve 90% power to detect a change in patient-level PPV of 0.13 using a one-sided binomial test at a targeted significance level of 2.5%. This sample size includes an adjustment for a dropout rate of 20%.

The lower bound of the 95% CI for patient-level PPV should be greater than 0.20 to be considered a success.

A total sample size of 190 participants can ensure 92.7% statistical power for region-level CLR and 90% statistical power for patient-level PPV resulting in an overall study statistical power of at least 83.4% (0.927\*0.90).

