#### 5.4 Statistical models

## 5.4.1 Analysis supporting primary objective(s)

For region-level CLR, statistical model details are presented in Section 2.5. The GLIMMIX procedure in SAS will be used to implement the logistic regression model with random effects.

This analysis will be restricted to participants with at least one PET positive region (TP or FP) by central assessments in the EFF. In case of problems with fitting the model and estimating parameters, the default estimation technique (i.e. residual pseudo-likelihood with a subject expansion (METHOD = RSPL)) will be used. This analysis will be applied to each of the three central readers via the (BY READER) statement.

For this model, the SAS code will be:

```
proc glimmix data=dataset;
by reader;
  class subject;
  model tpcount / poscount= / solution;
  random intercept / subject=subject;
run;
```

- tpcount refers to the number of TP regions per participant
- poscount refers to the number of PET positive regions (TP or FP) per participant

The estimated fixed effect  $\hat{\mu}$  and its standard error SE on the logit scale can be obtained from the output. And the (subject-specific) region-level CLR (conditional on the random effect when  $b_i = 0$ ) along with the two-sided 95% CI can be computed by applying the inverse link function:

Point estimate of the region-level CLR: 
$$E[p_{i}|\hat{b}_{i}=0] = E\left[\frac{y_{-}i}{n_{-}i}|\hat{b}_{i}=0\right] = \frac{\exp(\hat{\mu})}{1+\exp(\hat{\mu})}$$

$$CI_{Lower} = \frac{\exp(\hat{\mu}-z_{0.975}SE)}{1+\exp(\hat{\mu}-z_{0.975}SE)}$$

$$CI_{Upper} = \frac{\exp(\hat{\mu}+z_{0.975}SE)}{1+\exp(\hat{\mu}+z_{0.975}SE)}$$

For patient-level PPV, an exact binomial confidence interval (implemented using SAS procedure FREQ with EXACT statement for one-way tables) will be calculated (Clopper and Pearson 1934)

[figure not shown]
Efficacy endpoints be summarized in terms of percentage rates with 95% CIs.

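### The covariate-adjusted patient-level PPV model has no protection against a PSA band that is all true positive; penalised likelihood would be a cheap improvement

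*SAP*

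**What the plan says.** SAP 2.5.6 (Supplementary analyses) plans a logistic regression for patient-level PPV. The candidate covariates are baseline PSA in five bands (4 degrees of freedom) and initial definitive therapy, prostatectomy or radiation (1 degree of freedom). On testing it says: "The p-values from the Type III tests for each candidate covariate in the full model will be provided". PPV with a 95% CI for each covariate level is shown from the full model, and "the final model including only statistically significant covariates (p-value < 0.05), will be displayed" beside it. If no covariate is significant, the unadjusted estimate is given.

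Three things are not stated for this model: whether the Type III statistic is Wald, likelihood-ratio or score; which SAS procedure fits it (SAP 2.1 says only SAS 9.4 or later); and what happens if a band is all TP or has no TP. The one provision for fitting problems, in SAP 5.4.1, concerns the region-level CLR model.

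SAP Table 1-1 lists as a secondary objective "Evaluate the patient-level positive predictive value related to PSA levels". Its endpoint is a percentage stratified by PSA level. SAP 2.2.1 and 2.5.6 also plan PPV by PSA band as a subgroup analysis, and SAP 2.5.2 gives the exact Clopper-Pearson interval as the PPV method.

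**The concern.** About 122 PET-positive participants are spread over five PSA bands. If one band is all TP, its maximum-likelihood log-odds has no finite value (quasi-complete separation). The fitted coefficient stops wherever the iterations stop, with a huge standard error, and the model-based interval for that band carries no information.

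A Wald test gives that band almost no weight. One more TP in the best band can then move PSA from significant to non-significant. At stake is a supplementary table that could call PSA non-significant, omit it from the final model, and print a useless interval for the band with the clearest result.

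**Working it through.** **1. Denominator and the plan's own figure.** SAP 3.1 states "The null hypothesis (H0: patient-level PPV p = 0.20) will be tested" and "Assuming a patient-level PPV of 0.33 under the alternative hypothesis", at one-sided 2.5%, with 80% PET-positive and 20% dropout. PET-positive participants: 190 × 0.8 × 0.8 = 121.6, about 122. With n = 122 the exact binomial rule needs 34 TP, which gives one-sided alpha 0.0228 and power 0.905. The stated 90% is reproduced.

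**2. Worked example.** The documents give no PSA distribution, so the band sizes (sum 122) and TP counts are assumptions. For a model with PSA only, the joint Wald statistic is

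W = Σ w(l − l̄)², where l = ln[y/(n − y)], w = y(n − y)/n and l̄ = Σwl/Σw, on 4 df. Its p-value is exp(−W/2)(1 + W/2).

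| TP/n | l | w |
|---|---|---|
| 9/15 | 0.405 | 3.600 |
| 12/17 | 0.875 | 3.529 |
| 16/20 | 1.386 | 3.200 |
| 27/30 | 2.197 | 2.700 |
| 40/40 | infinite | 0 |
| 39/40, for comparison | 3.664 | 0.975 |

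- With 40/40 the last band drops out of the sum: l̄ = 14.918/13.029 = 1.145, W = 1.969 + 0.256 + 0.186 + 2.989 = 5.40, p = exp(−2.70) × 3.70 = 0.25.
- With 39/40: l̄ = 18.490/14.004 = 1.320, W = 11.16, p = exp(−5.58) × 6.58 = 0.025.
- Likelihood ratio with 40/40: the log-likelihood is −51.05 with one common PPV (104/122) and −40.15 with separate bands. Twice the difference is 21.8 and p = 0.0002.
- Firth penalised likelihood ratio with 40/40, computed numerically: p = 0.0007.

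**3. Interval for the separated band.** A numerical fit stopped at a coefficient of about 23 with standard error about 12,564. The back-transformed 95% interval is about 0 to 1. The exact lower limit for 40/40 is 0.025^(1/40) = 0.912.

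**4. Adding prior therapy.** Band sizes 24/24/24/24/26 with TP 14/17/19/21/26, and radiation patients placed only in the top two bands, gave PSA Wald p = 0.49 against likelihood-ratio p = 0.021.

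**5. How likely is an all-TP band?** For 24 participants the chance is PPV^24: about 0 at 0.33, 0.08 at 0.90, 0.29 at 0.95 and 0.62 at 0.98. For band sizes 15/17/20/30/40:

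| Assumed PPV by band | Overall PPV | Any all-TP band | Power, Wald | Power, Firth |
|---|---|---|---|---|
| 0.33 throughout | 0.33 | about 7 in 10⁸ | – | – |
| 0.45/0.55/0.60/0.70/0.75 | 0.65 | about 0.0001 | – | – |
| 0.60/0.70/0.80/0.90/0.97 | 0.84 | 33% | 0.60 | 0.91 |
| 0.70/0.80/0.85/0.93/0.98 | 0.89 | 55% | 0.27 | 0.75 |

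The power figures come from 6,000 simulated trials per scenario with PSA only. Firth size under the null was 0.02 to 0.05. In scenarios with overall PPV between about 0.33 and 0.62, separation was rare and the gain small (0.21 v 0.30; 0.51 v 0.55).

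**6. It is not inevitable.** With 7/15, 11/17, 16/20, 28/30, 40/40 the Wald p is 0.030. With 5/15, 9/17, 15/20, 27/30, 40/40 it is 0.006. PSA stays in both.

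**The case against.** The case against making much of this is strong, and most of it stands.

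- **The SAP does not say Wald.** A reader might infer that it prescribes a Wald test. It says only Type III. Wald is the usual PROC LOGISTIC output, but neither that procedure nor the statistic is named for this model. With a likelihood-ratio Type III test the same data keep PSA. The degenerate full-model interval does not depend on this point.
- **The PSA effect would not vanish from the report.** A reader might infer that it would. The full model is displayed whatever the p-value, and PPV by PSA band is a separate subgroup analysis. Under the stated PPV method the 0.912 limit for a 40/40 band would be expected there.
- **The named PSA objective does not rest on this test.** Its endpoint is descriptive, a percentage by PSA level, and no hypothesis test is attached to it.
- **The design values are far from the trouble.** It can be argued that 0.33 is only a testing value. The equal-weight CLR estimator cannot exceed PPV, so the CLR of 0.58 assumed in SAP 3.1 implies PPV of at least 0.58. That is correct, but at an overall PPV of about 0.65 an all-TP band is still practically absent.
- **The CLR covariate model.** SAP 5.4.1 says "The GLIMMIX procedure in SAS will be used to implement the logistic regression model with random effects", and a reader might carry the point over to that model. No calculation here covers it. Changing the estimation method for the adjusted CLR alone would also set it apart from the unadjusted CLR.

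What survives is that the p < 0.05 rule runs on an unpenalised fit, with the statistic unnamed and no provision for a separated band.

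**Conclusion.** The point holds as a cheap improvement to one supplementary analysis. It is not an error in the trial's conclusions: the co-primary tests, the success rule, the sample size and the power are unaffected.

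If a PSA band is all TP, the full-model interval for that band is uninformative whatever the test. If the Type III test is also Wald, PSA may be left out of the final model despite a strong effect (p = 0.25 against 0.0002 or 0.0007 in the example). In the two high-PPV scenarios a Wald test would have power 0.60 and 0.27, against 0.91 and 0.75 for Firth.

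These sizes rest on assumed band sizes, assumed PPVs by band and the Wald assumption. They matter only if PPV in some band reaches about 0.9 or more. It would be too strong to say that the rule discards the strongest PSA effects in general: steep gradients across the other bands survive it.

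**What to change.** In SAP 2.5.6, state that the covariate-adjusted patient-level PPV model is fitted by Firth penalised likelihood, with profile penalised-likelihood 95% CIs, and that the p < 0.05 rule uses the penalised likelihood-ratio test. This names the missing statistic and gives a finite estimate when a band is all TP or has no TP. No change is proposed for the CLR covariate model.

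The cost is a sentence in the SAP, a procedure option to program, and slight shrinkage; no new data are needed. With PSA alone in the model, Firth amounts to (y + 0.5)/(n + 1) per band: 9/15 moves from 0.600 to 9.5/16 = 0.594, 39/40 from 0.975 to 39.5/41 = 0.963, and 40/40 from 1 to 40.5/41 = 0.988.
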